#### Descriptive Summary

| Cancer Type | Visit   | Cycle Length | Average Dose[a] | STD   | Min | Median | Max |
|-------------|---------|--------------|-----------------|-------|-----|--------|-----|
| Melanoma    | Cycle 1 | q14d         | xxx.xx          | XX.XX | XXX | XXX.X  | XXX |
|             | Cycle 2 | q14d         | XXX.XX          | XX.XX | XXX | XXX.X  | XXX |
|             | Cycle 3 | q14d         | XXX.XX          | XX.XX | XXX | XXX.X  | XXX |
|             | Cycle 4 | q14d         | XXX.XX          | XX.XX | XXX | XXX.X  | XXX |
|             | Cycle 5 | q14d         | XXX.XX          | XX.XX | XXX | XXX.X  | XXX |
|             | Cycle 6 | q14d         | XXX.XX          | XX.XX | XXX | XXX.X  | XXX |

FOLDER\PROGRAM\OUTPUT: XXXXXXXXXXX.SAS\XXXXXX.LST

[a] Average dose (mg) = [total actual dose taken by each subject (mg) in a cycle]/[number of subjects with a nonzero dose in that cycle]

Abbreviations: Min = minimum; Max = maximum; STD = standard deviation.

DATABASE VERSION: XXXXX2016

DATE (TIME): MMDDYYYY (hh:mm)

PROTOCOL: INCAGN 1876-101

DRUG/INDICATION: INCAGN01876/Advanced or Metastatic Solid Tumors

TLF VERSION: Draft

Table 3.1.2.2

Summary of Study Drug Exposure by Visit (Population: Part 2 FAS Population)

#### Descriptive Summary

| Cancer Type | Visit   | Cycle Length | Average Dose[a] | STD   | Min | Median | Max |
|-------------|---------|--------------|-----------------|-------|-----|--------|-----|
| NSCLC       | Cycle 1 | q14d         | xxx.xx          | XX.XX | XXX | XXX.X  | XXX |
|             | Cycle 2 | q14d         | xxx.xx          | XX.XX | XXX | XXX.X  | XXX |
|             | Cycle 3 | q14d         | XXX.XX          | XX.XX | XXX | XXX.X  | XXX |
|             | Cycle 4 | q14d         | XXX.XX          | XX.XX | XXX | XXX.X  | XXX |
|             | Cycle 5 | q14d         | XXX.XX          | XX.XX | XXX | XXX.X  | XXX |
|             | Cycle 6 | q14d         | XXX.XX          | XX.XX | XXX | XXX.X  | XXX |

FOLDER\PROGRAM\OUTPUT: XXXXXX\XXXXXX.SAS\XXXXXX.LST

[a] Average dose (mg) = [total actual dose taken by each subject (mg) in a cycle]/[number of subjects with a nonzero dose in that cycle]

Abbreviations: Min = minimum; Max = maximum; STD = standard deviation.

DATABASE VERSION: XXXXX2016

DATE (TIME): MMDDYYYY (hh:mm)

PROTOCOL: INCAGN 1876-101

DRUG/INDICATION: INCAGN01876/Advanced or Metastatic Solid Tumors

TLF VERSION: Draft

Table 3.1.2.2

Summary of Study Drug Exposure by Visit (Population: Part 2 FAS Population)

#### Descriptive Summary

| Cancer Type | Visit   | Cycle Length | Average Dose[a] | STD   | Min | Median | Max |
|-------------|---------|--------------|-----------------|-------|-----|--------|-----|
| RCC         | Cycle 1 | q14d         | xxx.xx          | XX.XX | XXX | XXX.X  | XXX |
|             | Cycle 2 | q14d         | XXX.XX          | XX.XX | XXX | XXX.X  | XXX |
|             | Cycle 3 | q14d         | XXX.XX          | XX.XX | XXX | XXX.X  | XXX |
|             | Cycle 4 | q14d         | XXX.XX          | XX.XX | XXX | XXX.X  | XXX |
|             | Cycle 5 | q14d         | XXX.XX          | XX.XX | XXX | XXX.X  | XXX |
|             | Cycle 6 | q14d         | XXX.XX          | XX.XX | XXX | XXX.X  | XXX |

FOLDER\PROGRAM\OUTPUT: XXXXXXX\XXXXXX.SAS\XXXXXX.LST

[a] Average dose (mg) = [total actual dose taken by each subject (mg) in a cycle]/[number of subjects with a nonzero dose in that cycle]

Abbreviations: Min = minimum; Max = maximum; STD = standard deviation.

PROTOCOL: INCAGN 1876-101

(Page n of N)
DATABASE VERSION: XXXXX2016

DATE (TIME): MMDDYYYY (hh:mm)

DRUG/INDICATION: INCAGN01876/Advanced or Metastatic Solid Tumors

TLF VERSION: Draft

Table 3.2.1.1

Overall Summary of Treatment-Emergent Adverse Events (Population: Part 1 FAS Population)

|   |                | Dose Lev       | el (mg/kg)    |               |
|---|----------------|----------------|---------------|---------------|
|   | 0.01
(N=xx) | 0.03
(N=xx) | 0.1
(N=xx) | 0.3
(N=xx) |
| Subjects who had a TEAE                     | xx (xx.x)      | xx (xx.x)      | xx (xx.x)     | xx (xx.x)     |
| Subjects who had a treatment-related TEAE   | xx (xx.x)      | xx (xx.x)      | xx (xx.x)     | xx (xx.x)     |
| Subjects who had a SAE                      | xx (xx.x)      | xx (xx.x)      | xx (xx.x)     | xx (xx.x)     |
| Subjects who had an AE of grade 3 or higher | xx (xx.x)      | xx (xx.x)      | xx (xx.x)     | xx (xx.x)     |
| Subjects who had a fatal AE                 | xx (xx.x)      | xx (xx.x)      | xx (xx.x)     | xx (xx.x)     |
| Subjects who had AE leading to              | xx (xx.x)      | xx (xx.x)      | xx (xx.x)     | xx (xx.x)     |
| discontinuation of study medication         |                |                |               |               |
| Subjects who had a DLT                      | xx (xx.x)      | xx (xx.x)      | xx (xx.x)     | xx (xx.x)     |
| Subjects who had an irAE                    | xx (xx.x)      | xx (xx.x)      | xx (xx.x)     | xx (xx.x)     |
| Subjects who had a Grade 3 or higher irAE   | xx (xx.x)      | xx (xx.x)      | xx (xx.x)     | xx (xx.x)     |

FOLDER\PROGRAM\OUTPUT: XXXXXX\XXXXXX.SAS\XXXXXX.LST

Immune-Related Adverse Event: any AE consistent with an immune phenomenon associated with drug exposure after all other etiologies have been eliminated.

Treatment-Emergent Adverse Event: any AE either reported for the first time or worsening of a pre-existing event after first dose of study medication.

Treatment-Related Adverse Events: treatment-emergent adverse events judged as related by the investigator or with a missing causality.

DATABASE VERSION: XXXXX2016

DATE (TIME): MMDDYYYY (hh:mm)

PROTOCOL: INCAGN 1876-101

DRUG/INDICATION: INCAGN01876/Advanced or Metastatic Solid Tumors

TLF VERSION: Draft

Table 3.2.1.1

Overall Summary of Treatment-Emergent Adverse Events (Population: Part 1 FAS Population)

|   |               | Dose Lev      | el (mg/kg)    |                |       |
|---|---------------|---------------|---------------|----------------|-------|
|   | 1.0
(N=xx) | 3.0
(N=xx) | 5.0
(N=xx) | 10.0
(N=xx) | Total |
| Subjects who had a TEAE   | xx (xx.x)     | xx (xx.x)     | xx (xx.x)     | xx (xx.x)      |       |
| Subjects who had a treatment-related TEAE                             | xx (xx.x)     | xx (xx.x)     | xx (xx.x)     | xx (xx.x)      |       |
| Subjects who had a SAE  | xx (xx.x)     | xx (xx.x)     | xx (xx.x)     | xx (xx.x)      |       |
| Subjects who had an AE of grade 3 or higher                           | xx (xx.x)     | xx (xx.x)     | xx (xx.x)     | xx (xx.x)      |       |
| Subjects who had a fatal AE   | xx (xx.x)     | xx (xx.x)     | xx (xx.x)     | xx (xx.x)      |       |
| Subjects who had AE leading to
discontinuation of study medication | xx (xx.x)     | xx (xx.x)     | xx (xx.x)     | xx (xx.x)      |       |
| Subjects who had a DLT  | xx (xx.x)     | xx (xx.x)     | xx (xx.x)     | xx (xx.x)      |       |
| Subjects who had an irAE  | xx (xx.x)     | xx (xx.x)     | xx (xx.x)     | xx (xx.x)      |       |
| Subjects who had a Grade 3 or higher irAE                             | xx (xx.x)     | xx (xx.x)     | xx (xx.x)     | xx (xx.x)      |       |

FOLDER\PROGRAM\OUTPUT: XXXXXX\XXXXXX.SAS\XXXXXX.LST

Immune-Related Adverse Event: any AE consistent with an immune phenomenon associated with drug exposure after all other etiologies have been eliminated.

Treatment-Emergent Adverse Event: any AE either reported for the first time or worsening of a pre-existing event after first dose of study medication.

Treatment-Related Adverse Events: treatment-emergent AEs judged as related by the investigator or with a missing causality.

DATABASE VERSION: XXXXX2016

DATE (TIME): MMDDYYYY (hh:mm)

PROTOCOL: INCAGN 1876-101

DRUG/INDICATION: INCAGN01876/Advanced or Metastatic Solid Tumors

TLF VERSION: Draft

Table 3.2.1.2

Overall Summary of Treatment-Emergent Adverse Events (Population: Part 2 FAS Population)

|   |                    | Cano                    | cer Type        |               |              |
|---|--------------------|-------------------------|-----------------|---------------|--------------|
|   | Endomet:
(N=xx) | rium Melanoma
(N=xx) | NSCLC
(N=xx) | RCC
(N=xx) | Total (N=xx) |
| Subjects who had a TEAE   | xx (xx.            | x) xx (xx.x)            | xx (xx.x)       | xx (xx.x)     |              |
| Subjects who had a treatment-related TEAE                             | xx (xx.            | x) xx (xx.x)            | xx (xx.x)       | xx (xx.x)     |              |
| Subjects who had a SAE  | xx (xx.            | x) xx (xx.x)            | xx (xx.x)       | xx (xx.x)     |              |
| Subjects who had an AE of grade 3 or higher                           | xx (xx.            | x) xx (xx.x)            | xx (xx.x)       | xx (xx.x)     |              |
| Subjects who had a fatal AE   | xx (xx.            | x) xx (xx.x)            | xx (xx.x)       | xx (xx.x)     |              |
| Subjects who had AE leading to
discontinuation of study medication | xx (xx.            | x) xx (xx.x)            | xx (xx.x)       | xx (xx.x)     |              |
| Subjects who had a DLT  | xx (xx.            | x) xx (xx.x)            | xx (xx.x)       | xx (xx.x)     |              |
| Subjects who had an irAE  | xx (xx.            | x) xx (xx.x)            | xx (xx.x)       | xx (xx.x)     |              |
| Subjects who had a Grade 3 or higher irAE                             | xx (xx.            | x) xx (xx.x)            | xx (xx.x)       | xx (xx.x)     |              |

FOLDER\PROGRAM\OUTPUT: XXXXXX\XXXXXX.SAS\XXXXXX.LST

Immune-Related Adverse Event: any AE consistent with an immune phenomenon associated with drug exposure after all other etiologies have been eliminated.

Treatment-Emergent Adverse Event: any AE either reported for the first time or worsening of a pre-existing event after first dose of study medication.

Treatment-Related AEs: treatment-emergent AEs judged as related by the investigator or with a missing causality.

PROTOCOL: INCAGN 1876-101 (Page n of N) DRUG/INDICATION: INCAGN01876/Advanced or Metastatic Solid Tumors DATABASE VERSION: XXXXX2016

TLF VERSION: Draft

Table 3.2.2.1

Summary of Treatment-Emergent Adverse Events by MedDRA System Organ Class and Preferred Term (Population: Part 1 FAS Population)

|   |           | Dose Lev  | el (mg/kg)    |               |  |
|---|-----------|-----------|---------------|---------------|--|
| MedDRA System Organ Class/
MedDRA Preferred Term |           |           | 0.1
(N=xx) | 0.3
(N=xx) |  |
| Number (%) of subjects with any                     | xx (xx.x) | xx (xx.x) | xx (xx.x)     | xx (xx.x)     |  |
| Treatment-Emergent Adverse Events                   |           |           |               |               |  |
| System Organ Class 1                                | xx (xx.x) | xx (xx.x) | xx (xx.x)     | xx (xx.x)     |  |
| Preferred term 1                                    | xx (xx.x) | xx (xx.x) | xx (xx.x)     | xx (xx.x)     |  |
| Preferred term 2                                    | xx (xx.x) | xx (xx.x) | xx (xx.x)     | xx (xx.x)     |  |
| Preferred term 3                                    | xx (xx.x) | xx (xx.x) | xx (xx.x)     | xx (xx.x)     |  |
| •••   | xx (xx.x) | xx (xx.x) | xx (xx.x)     | xx (xx.x)     |  |
| System Organ Class 2                                | xx (xx.x) | xx (xx.x) | xx (xx.x)     | xx (xx.x)     |  |
| Preferred term 1                                    | xx (xx.x) | xx (xx.x) | xx (xx.x)     | xx (xx.x)     |  |
| Preferred term 2                                    | xx (xx.x) | xx (xx.x) | xx (xx.x)     | xx (xx.x)     |  |
| Preferred term 3                                    | xx (xx.x) | xx (xx.x) | xx (xx.x)     | xx (xx.x)     |  |
| •••   | xx (xx.x) | xx (xx.x) | xx (xx.x)     | xx (xx.x)     |  |
| System Organ Class 3                                | xx (xx.x) | xx (xx.x) | xx (xx.x)     | xx (xx.x)     |  |
| Preferred term 1                                    | xx (xx.x) | xx (xx.x) | xx (xx.x)     | xx (xx.x)     |  |
|   | xx (xx.x) | xx (xx.x) | xx (xx.x)     | xx (xx.x)     |  |

FOLDER\PROGRAM\OUTPUT: XXXXXXXXXXXX.SAS\XXXXXX.LST

Treatment-Emergent Adverse Event: any AE either reported for the first time or worsening of a pre-existing event after first dose of study medication.

Note 1: Subjects were counted once under each MedDRA system organ class and preferred term.

PROTOCOL: INCAGN 1876-101 (Page n of N)
DRUG/INDICATION: INCAGN01876/Advanced or Metastatic Solid Tumors DATABASE VERSION: XXXXX2016

TLF VERSION: Draft

Table 3.2.2.1

Summary of Treatment-Emergent Adverse Events by MedDRA System Organ Class and Preferred Term (Population: Part 1 FAS Population)

|   |               | Dose Lev      | el (mg/kg)    |                |              |  |
|---|---------------|---------------|---------------|----------------|--------------|--|
| MedDRA System Organ Class/
MedDRA Preferred Term | 1.0
(N=xx) | 3.0
(N=xx) | 5.0
(N=xx) | 10.0
(N=xx) | Total (N=xx) |  |
| Number (%) of subjects with any                     | xx (xx.x)     | xx (xx.x)     | xx (xx.x)     | xx (xx.x)      | xx (xx.x)    |  |
| Treatment-Emergent Adverse Events                   |               |               |               |                |              |  |
| System Organ Class 1                                | xx (xx.x)     | xx (xx.x)     | xx (xx.x)     | xx (xx.x)      | xx (xx.x)    |  |
| Preferred term 1                                    | xx (xx.x)     | xx (xx.x)     | xx (xx.x)     | xx (xx.x)      | xx (xx.x)    |  |
| Preferred term 2                                    | xx (xx.x)     | xx (xx.x)     | xx (xx.x)     | xx (xx.x)      | xx (xx.x)    |  |
| Preferred term 3                                    | xx (xx.x)     | xx (xx.x)     | xx (xx.x)     | xx (xx.x)      | xx (xx.x)    |  |
| • • •   | xx (xx.x)     | xx (xx.x)     | xx (xx.x)     | xx (xx.x)      | xx (xx.x)    |  |
| System Organ Class 2                                | xx (xx.x)     | xx (xx.x)     | xx (xx.x)     | xx (xx.x)      | xx (xx.x)    |  |
| Preferred term 1                                    | xx (xx.x)     | xx (xx.x)     | xx (xx.x)     | xx (xx.x)      | xx (xx.x)    |  |
| Preferred term 2                                    | xx (xx.x)     | xx (xx.x)     | xx (xx.x)     | xx (xx.x)      | xx (xx.x)    |  |
| Preferred term 3                                    | xx (xx.x)     | xx (xx.x)     | xx (xx.x)     | xx (xx.x)      | xx (xx.x)    |  |
| •••   | xx (xx.x)     | xx (xx.x)     | xx (xx.x)     | xx (xx.x)      | xx (xx.x)    |  |
| System Organ Class 3                                | xx (xx.x)     | xx (xx.x)     | xx (xx.x)     | xx (xx.x)      | xx (xx.x)    |  |
| Preferred term 1                                    | xx (xx.x)     | xx (xx.x)     | xx (xx.x)     | xx (xx.x)      | xx (xx.x)    |  |
|   | xx (xx.x)     | xx (xx.x)     | xx (xx.x)     | xx (xx.x)      | xx (xx.x)    |  |

FOLDER\PROGRAM\OUTPUT: XXXXXXXXXXXX.SAS\XXXXXX.LST

Treatment-Emergent Adverse Event: any AE either reported for the first time or worsening of a pre-existing event after first dose of study medication.

Note 1: Subjects were counted once under each MedDRA system organ class and preferred term.

DATABASE VERSION: XXXXX2016

DATE (TIME): MMDDYYYY (hh:mm)

PROTOCOL: INCAGN 1876-101

DRUG/INDICATION: INCAGN01876/Advanced or Metastatic Solid Tumors

TLF VERSION: Draft

Table 3.2.2.2

Summary of Treatment-Emergent Adverse Events by MedDRA System Organ Class and Preferred Term (Population: Part 2 FAS Population)

|   |           | Canc              | er Type         |               |              |
|---|-----------|-------------------|-----------------|---------------|--------------|
| MedDRA System Organ Class/
MedDRA Preferred Term |           | m Melanoma (N=xx) | NSCLC
(N=xx) | RCC
(N=xx) | Total (N=xx) |
| Number (%) of subjects with any                     | xx (xx.x) | xx (xx.x)         | xx (xx.x)       | xx (xx.x)     | XX           |
| Treatment-Emergent Adverse Events                   | (,        | (,                | ( /             | (,            |              |
| System Organ Class 1                                | xx (xx.x) | xx (xx.x)         | xx (xx.x)       | xx (xx.x)     | xx (xx.x)    |
| Preferred term 1                                    | xx (xx.x) | xx (xx.x)         | xx (xx.x)       | xx (xx.x)     | xx (xx.x)    |
| Preferred term 2                                    | xx (xx.x) | xx (xx.x)         | xx (xx.x)       | xx (xx.x)     | xx (xx.x)    |
| Preferred term 3                                    | xx (xx.x) | xx (xx.x)         | xx (xx.x)       | xx (xx.x)     | xx (xx.x)    |
| •••   | xx (xx.x) | xx (xx.x)         | xx (xx.x)       | xx (xx.x)     | xx (xx.x)    |
| System Organ Class 2                                | xx (xx.x) | xx (xx.x)         | xx (xx.x)       | xx (xx.x)     | xx (xx.x)    |
| Preferred term 1                                    | xx (xx.x) | xx (xx.x)         | xx (xx.x)       | xx (xx.x)     | xx (xx.x)    |
| Preferred term 2                                    | xx (xx.x) | xx (xx.x)         | xx (xx.x)       | xx (xx.x)     | xx (xx.x)    |
| Preferred term 3                                    | xx (xx.x) | xx (xx.x)         | xx (xx.x)       | xx (xx.x)     | xx (xx.x)    |
| •••   | xx (xx.x) | xx (xx.x)         | xx (xx.x)       | xx (xx.x)     | xx (xx.x)    |
| System Organ Class 3                                | xx (xx.x) | xx (xx.x)         | xx (xx.x)       | xx (xx.x)     | xx (xx.x)    |
| Preferred term 1                                    | xx (xx.x) | xx (xx.x)         | xx (xx.x)       | xx (xx.x)     | xx (xx.x)    |
| • • •   | xx (xx.x) | xx (xx.x)         | xx (xx.x)       | xx (xx.x)     | xx (xx.x)    |

FOLDER\PROGRAM\OUTPUT: XXXXXX\XXXXXX.SAS\XXXXXX.LST

Treatment-Emergent Adverse Event: any AE either reported for the first time or worsening of a pre-existing event after first dose of study medication.

Note 1: Subjects were counted once under each MedDRA system organ class and preferred term.

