beginning with Cohort 1 (0.03 mg/kg; starting dose). There will be a waiting period of 48 hours between dose administration of the first subject and second subject of each dose cohort. The first 3 subjects enrolled within a cohort will be observed for a DLT observation period of 28 days before the next cohort begins enrollment. The dose will be escalated if 0 of the first 3 evaluable subjects enrolled has a DLT. If 1 of the first 3 evaluable subjects enrolled has a DLT, then the cohort will be expanded to include 3 additional evaluable subjects, and if no DLT occurs in the additional 3 subjects, then the dose will be escalated. If a DLT occurs in one-third or more of the expanded cohort, then the MTD will be deemed to be exceeded, and the prior dose level will be considered the MTD. If only 3 subjects were treated at the MTD or PAD, then a minimum of 3 additional subjects will be enrolled before this dose is administered in Part 2 of the study.

If Cohort 1 (0.03 mg/kg; starting dose) exceeds the MTD, the sponsor and investigators will consider dosing INCAGN01876 at 0.01 mg/kg (Cohort -1), and/or investigate 0.03 mg/kg at alternate dose schedules, based on available safety, PK, data. If an alternate schedule is tested and determined to be safe, re-escalation of INCAGN01876 will proceed according to Table 1.

Throughout the treatment period, if > 33% of subjects (a minimum of 6 subjects) experience a  $\ge$  Grade 3 toxicity related to study drug after completing  $\ge$  4 cycles, then dose administration will be stopped, and the MNTD will be determined in conjunction with the investigators and sponsor based on all available safety data.

[figure not shown]
Additional subjects will be enrolled in a cohort to achieve the minimum of 3 evaluable subjects. Subjects who drop out for reasons other than a DLT (eg, events clearly associated with the underlying disease, disease progression, concomitant medication, or comorbidity) during the 28-day DLT observation period will be considered nonevaluable and will be replaced. Dose modifications should not be made during the DLT observation period without discussion with the medical monitor. Intrasubject dose escalation is not permitted; however, once the RP2D and schedule has been determined, ongoing subjects in Part 1 may be permitted to escalate to the RP2D with approval of the medical monitor. The cohorts and dose levels are shown in Table 1.

| Table 1. | INCAGN01876 Dose I    | l ovole and | Caharte |

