#### 3.1.2. Part 1 – Safety Expansion

Approximately 36 evaluable subjects will be enrolled in the Part 1 safety expansion, and each safety expansion cohort will enroll approximately 9 evaluable subjects. If < 3 of 9 evaluable subjects experience a DLT, then the cohort will be deemed safe. If > 1 safety expansion cohort is deemed safe, then the RP2D and schedule will be determined in conjunction with the investigators and sponsor based on all available safety, PK, results. At the sponsor's discretion, the safety expansion cohorts may be conducted in parallel to Part 2 and may be limited to subjects with specific tumor types to achieve a balance across cohorts.

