## 5.3.2. Part 1 Full Analysis Set Population

The Part 1 FAS population includes all subjects in the FAS population enrolled in Part 1 of the study who received at least 1 dose of INCAGN01876.

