## 5.3.3. Part 2 Full Analysis Set Population

The Part 2 FAS population includes all subjects in the FAS population enrolled in Part 2 of the study who received at least 1 dose of the MTD/PAD of INCAGN01876. Subjects tested in the Part 1 (dose escalation and safety expansion) who are treated at the MTD/PAD and in Part 2, who are of the same tumor type, and who meet inclusion/exclusion criteria used for the tumor type of interest in Part 2 will be combined for both safety and efficacy summary purposes.

Specific analysis populations to be used for evaluating the Simon 2-stage efficacy rules include the following subgroups:

- Part 2 FAS population subjects with adenocarcinoma of endometrium
- Part 2 FAS population subjects with melanoma
- Part 2 FAS population subjects with NSCLC
- Part 2 FAS population subjects with RCC

Table summaries, unless otherwise indicated, will be provided by tumor-specific cohort.

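### The Part 2 safety tables pool in Part 1 subjects whose dose had to meet DLT limits, so the Part 2 DLT percentage is biased low, by an amount that depends on how many are pooled

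*SAP*

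**What the plan says.** SAP 5.3.3 opens by defining the Part 2 FAS as treated subjects enrolled in Part 2. It then adds "Subjects tested in the Part 1 (dose escalation and safety expansion) who are treated at the MTD/PAD and in Part 2", of the same tumor type, "who meet inclusion/exclusion criteria used for the tumor type of interest in Part 2 will be combined for both safety and efficacy summary purposes". Protocol 9.1, which defines the analysis populations, describes no such pooling.

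The Part 2 adverse event shells in SAP Appendix A (Tables 3.2.1.2 to 3.2.21.2, and the life table 3.2.22) all carry the Part 2 FAS label. Table 3.2.1.2, headed "Overall Summary of Treatment-Emergent Adverse Events (Population: Part 2 FAS Population", includes the row "Subjects who had a DLT" by tumor type. No listed shell is restricted to subjects enrolled in Part 2.

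SAP 5.3.2 leaves the pooled subjects in Part 1 as well: "The Part 1 FAS population includes all subjects in the FAS population enrolled in Part 1 of the study".

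On how a dose gets to Part 2, SAP 3.1.1 says "The dose will be escalated if 0 of the first 3 evaluable subjects enrolled has a DLT", with expansion to six after one DLT in three and escalation only if none of the added three has one. SAP 3.1.2 says of the expansion: "If < 3 of 9 evaluable subjects experience a DLT, then the cohort will be deemed safe". A footnote to SAP Figure 1 takes the Part 2 dose from the safety-expansion doses and schedules explored.

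**The concern.** Safety is the primary endpoint, and Part 2 is there to examine it further at the recommended dose. A table does that independently only if its subjects were not part of the evidence that let the dose through. The Part 1 subjects whom SAP 5.3.3 brings in were treated at a dose that had to show few DLTs in those same subjects. Their DLT count is capped by the rule, so they are not a fair sample of toxicity at that dose. Mixing them with Part 2 subjects pulls the DLT percentage down, and by more when the dose is truly too toxic. A reader of the Part 2 column cannot separate the two sources, because neither a Part 2-enrolled rate nor the number pooled is shown.

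**Working it through.** **Inputs.** The DLT limits are from SAP 3.1.1 and 3.1.2. Part 2 cohort sizes are 9 (Stage 1) and 17 (full), with up to 68 in all (Protocol 4.3.1). The number of Part 1 subjects pooled, m, is not given. At one dose it can range from 0 to 15 (6 escalation + 9 expansion), limited to matching tumor types. I assume independent DLTs, one true rate p in both Parts, and DLT-evaluable subjects only.

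**Plan's own figure.** SAP Table 2 gives the chance that a dose is declared safe.
- 3 + 3: (1−p)³ + 3p(1−p)²·(1−p)³. At p = 20% this is 0.5120 + 0.1966 = 70.9%.
- Expansion: P(X ≤ 2), X ~ Binomial(9, p). At 20% this is 0.7382.
- Both: 0.7086 × 0.7382 = 52.3%. The same steps give 22.9% at p = 30% and 7.2% at 40%.

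All 12 cells of Table 2 reproduce.

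**DLT rate in Part 1 subjects, given that the limits were met.** For the nine expansion subjects the rate is E[X | X ≤ 2]/9.
- p = 20%: (0.3020 + 2 × 0.3020)/0.7382 = 1.227 DLTs, or 13.6%.
- p = 30%: (0.1557 + 2 × 0.2668)/0.4628 = 1.489, or 16.5%.
- p = 40%: (0.0605 + 2 × 0.1612)/0.2318 = 1.652, or 18.4%.

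For the six escalation subjects there are two variants, because the SAP sets no separate DLT rule for the three subjects added after 0 of 3. With no rule on them the rate is 11.9% (p = 20%) and 15.5% (p = 30%). With at most 1 of 6 required it is 10.0% and 12.0%. All fifteen together give 12.2% to 12.9% at p = 20% and 14.7% to 16.1% at p = 30%.

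**Bias in the pooled column.** With r the conditional rate and n the Part 2-enrolled subjects, the pooled rate is (n·p + m·r)/(n + m), so the bias is m(r − p)/(n + m). Example: 3 expansion subjects into 17 at p = 20% gives 3 × (13.64 − 20)/20 = −0.95 points. The ranges below run from expansion subjects only to a mix of both sources; the row for 15 spans the two escalation variants.

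| Part 1 pooled into Part 2 | Understatement, true 20% | Understatement, true 30% |
|---|---|---|
| 0 into any cohort | 0 | 0 |
| 3 into 17 | 1.0 to 1.2 points | 2.0 to 2.3 |
| 9 into 17 | 2.2 to 2.7 | 4.7 to 5.3 |
| 15 into 17 | 3.3 to 3.7 | 6.5 to 7.2 |
| 3 into 9 | 1.6 to 2.0 | 3.4 to 3.8 |
| 9 into 9 | 3.2 to 3.9 | 6.7 to 7.6 |
| 3 into all-tumor 68 | 0.3 | 0.6 |
| 9 into all-tumor 68 | 0.7 to 0.9 | 1.6 to 1.8 |

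At a true 40%, nine expansion subjects pooled with nine give 9 × (18.36 − 40)/18 = −10.8 points (29.2% shown). Pooled with 17 they give −7.5 points (32.5% shown).

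**If the expansion runs in parallel with Part 2.** Where the nine are not read before the dose is set, their expected rate is p and they add no bias. Only the escalation subjects then contribute.

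**With the fix.** Part 2-enrolled subjects alone have expectation p, so these limits introduce no bias.

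**The case against.** The strongest reply has four parts.

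- **Dose choice.** A reader might infer that the low DLT count is why the dose was chosen. The documents do not support that. SAP 3.1.2 rests the recommended dose on all available safety and PK data among other results, and SAP 3.4.1 lets the PAD stand in for the MTD. Meeting the DLT limits is a necessary condition, not the reason. This narrows the wording, but conditioning on a necessary DLT limit still lowers the expected rate.
- **Parallel expansion.** SAP 3.1.2 and Protocol 4.1.2 allow the expansion to run alongside Part 2, so the 3-of-9 limit may not condition those subjects. This stands and reduces the size.
- **Size.** A reader might take 5 to 11 points as the general effect. That needs about nine pooled subjects of one Part 2 tumor type and a true rate of 30% to 40%, which meets both limits only 22.9% or 7.2% of the time. Part 1 takes any solid tumor, so few subjects may match. At 40%, two or more DLTs in six Part 2 subjects has probability 1 − 0.0467 − 0.1866 = 77%, which reaches the interruption threshold in Protocol 4.1.3 and SAP 3.1.3. This also stands.
- **Other displays.** Part 1 is summarized separately (SAP 8.1), DLTs are listed by dose and schedule (SAP 8.2.2, Listing 2.6.3), and Appendix A is only a guideline. None of these commits to a Part 2-enrolled rate.

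It can also be said that the combining sentence in SAP 5.3.3 does not expressly redefine the Part 2 FAS. But it sits in that definition, names safety summaries, and has no separate pooled shell, so the tables inherit it as written. If something else was meant, the section needs the same edit.

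**Conclusion.** The point holds for the DLT row. Pooling under SAP 5.3.3 biases the Part 2 DLT percentage low whenever subjects conditioned on the DLT limits are included. For a 17-subject cohort the plausible size is from nothing to about 5 points, depending on the number pooled and the true rate. Figures near 11 points need an extreme: a whole expansion cohort of one tumor type, a Part 2 cohort at nine, and a true rate of 40%. Pooling all fifteen Part 1 subjects into one cohort would go further still, but needs every one of them to share that tumor type. In the all-tumor total the effect is under 1 point with three pooled at either rate. These sizes rest on independent DLTs, equal true rates across Parts and tumor types, and an assumed number pooled.

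Two further readings are tempting and go too far. One is that every Part 2 adverse event row is biased in the same way. For Grade 3 or higher and related events the effect is indirect, through the DLTs they contain, and it is not quantified here. The other is that subjects are double-counted within a table. They are not. A pooled subject appears once in the Part 1 table and once in the Part 2 table, which misleads only if a reader adds the two totals. Still, no adverse event shell counts each treated subject once, although SAP 5.2 says data are summarized overall.

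**What to change.** In SAP 5.3.3 and shells 3.2.1.2 to 3.2.22:

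- Make subjects enrolled in Part 2 the main Part 2 safety columns, including the DLT row.
- Show the Part 1 + Part 2 pool at the same dose and schedule as a separate column, labelled supportive, with the number of Part 1 subjects stated.
- Add one all-treated FAS column in which each subject counts once.

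The cost is SAP wording and extra columns, and each main Part 2 column holds fewer subjects. No information is lost, because the pool stays visible beside it.
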